8.2.4.3. Systemic Events

During the reactogenicity e-diary reporting period, participants or participants' parent(s)/legal guardians will be asked to assess vomiting, diarrhea, headache, fatigue, chills, new or worsened muscle pain, and new or worsened joint pain and to record the symptoms in the reactogenicity e-diary. The symptoms will be assessed as absent, mild, moderate, or severe according to the grading scale in Table 5.

If a Grade 3 systemic event is reported in the reactogenicity e-diary, a telephone contact should occur to ascertain further details and determine whether a site visit is clinically indicated. Only an investigator or medically qualified person can classify a participant's systemic event as Grade 4. If a participant experiences a confirmed Grade 4 systemic event, the investigator must immediately notify the sponsor and, if it is determined to be related to the administration of the study intervention, further vaccinations will be discontinued in that participant.

Table 5. Systemic Event Grading Scale for All Study Participants

	Mild (Grade 1)	Moderate (Grade 2)	Severe (Grade 3) ^a	Potentially Life-Threatening (Grade 4) ^b
Vomiting	1-2 times in 24 hours	>2 times in 24 hours	Requires IV hydration	Emergency room visit or hospitalization for hypotensive shock
Diarrhea	2 to 3 loose stools in 24 hours	4 to 5 loose stools in 24 hours	6 or more loose stools in 24 hours	Emergency room visit or hospitalization for severe diarrhea
Headache	Does not interfere with activity	Some interference with activity	Prevents daily routine activity	Emergency room visit or hospitalization for severe headache
Fatigue/tiredness	Does not interfere with activity	Some interference with activity	Prevents daily routine activity	Emergency room visit or hospitalization for severe fatigue
Chills	Does not interfere with activity	Some interference with activity	Prevents daily routine activity	Emergency room visit or hospitalization for severe chills
New or worsened muscle pain	Does not interfere with activity	Some interference with activity	Prevents daily routine activity	Emergency room visit or hospitalization for severe new or worsened muscle pain

Table 5. Systemic Event Grading Scale for All Study Participants

	Mild (Grade 1)	Moderate (Grade 2)	Severe (Grade 3) ^a	Potentially Life-Threatening (Grade 4) ^b

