- When an AE or SAE occurs, it is the responsibility of the investigator to review all documentation (eg, hospital progress notes, laboratoly repolis, and diagnostic repolis) related to the event.
- The investigator will then record all relevant AE or SAE info 1 mation in the CRF.
- It is **not** acceptable for the investigator to send photocopies of the pailicipant's medical records to Pfizer Safety in lieu of completion of the Vaccine SAE Repoliing Fonn/AE or SAE CRF page.
- There may be instances when copies of medical records for celiain cases are requested by Pfizer Safety. In this case, all participant identifiers, with the exception of the pailicipant number, will be redacted on the copies of the medical records before submission to Pfizer Safety.
- The investigator will attempt to establish a diagnosis of the event based on signs, symptoms, and/or other clinical infolmation. Whenever possible, the diagnosis (not the individual signs/symptoms) will be documented as the AE or SAE.

Assessment of Intensity

The investigator will make an assessment of intensity for each AE and SAE repolied during the study and assign it to 1 of the following categories:

GRADE	If required on the AE page of the CRF, the investigator will use the adjectives MILD, MODERATE, SEVERE, or LIFE-THREATENING to describe the maximum intensity of the AE. For pmposes of consistency, these intensity grades are defined as follows:	
1	MILD	Does not interfere with pailicipant's usual function.
2	MODERATE	Interferes to some extent with pailicipant's usual function.
3	SEVERE	Interferes significantly with pailicipant's usual function.
4	LIFE-THREATENING	Life-threatening consequences; urgent intervention indicated.

Final Protocol Amendment 5. 13 Janualy 2023

Assessment of Causality

- The investigator is obligated to assess the relationship between study intervention and each occmTence of each AE or SAE. The investigator will use clinical judgment to detennine the relationship.
- A "reasonable possibility" of a relationship conveys that there are facts, evidence, and/or argmnents to suggest a causal relationship, rather than a relationship cannot be rnled out.
- Alternative causes, such as underlying disease(s), concomitant therapy, and other risk factors, as well as the temporal relationship of the event to study intervention administration, will be considered and investigated.

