3.1.2.1. Local Reactions

The local reactions assessed and reported in the e-diary are redness, swelling, and pain at the injection site, from Day 1 through Day 7 after each dose, where Day 1 is the day of each dose. The e-diary entries from the participant and unplanned clinical assessments within 7 days after vaccination will be the primary data source for these events. In addition, any AEs recorded on the AE CRF that are considered local reactions within 7 days after vaccination will be consolidated with e-diary data and included in the reactogenicity report.

This section describes derivations with details for the assessment of local reactions: presence, severity level, duration, and onset day.

PFIZER GENERAL BUSINESS

Presence or Absence

For each local reaction and any local reaction on any day, Table 3 explains the algorithm to derive the presence of a reaction (yes or no) during the interval from Day 1 through Day 7, where Day 1 is the day of each dose.

Table 3. Derived Variables for Presence of Each and Any Local Reaction Within 7 Days for Each Dose

Variable	Yes (1)	No (0)
Presence of each local reaction.	Participant reports the reaction as "yes" on any day (Day 1 through Day 7).	Participant reports the reaction as "no" on all 7 days (Day 1 through Day 7) or as a combination of "no" and missing on all 7 days (Day 1 through Day 7).
Presence of any local reaction.	Participant reports any local reaction as "yes" on any day (Day 1 through Day 7).	For all 3 local reactions, participant reports "no" on all 7 days (Day 1 through Day 7) or as a combination of "no" and missing on all 7 days (Day 1 through Day 7).

Severity and Maximum Severity

Redness and swelling will be measured and recorded in measuring device units (range: 1 to 21) and then categorized during analysis as absent, mild, moderate, or severe based on the grading scales in Table 4 and Table 5. Measuring device units can be converted to centimeters according to the following formula: 1 measuring device unit = 0.5 cm. Pain at the injection site will be assessed by the participant as absent, mild, moderate, or severe according to the grading scales in Table 4 and Table 5.

For events recorded in the AE CRF that are considered local reactions and consolidated with e-diary data, the severity will be based on the AE intensity grade recorded in the CRF.

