If redness or swelling >14 measuring device units is reported in the reactogenicity e-diary, regardless of the participant's age, a telephone contact should occur to ascertain further details and determine whether a site visit is clinically indicated. If Grade 3 pain at the injection site is reported in the reactogenicity e-diary, a telephone contact should occur to ascertain further details and determine whether a site visit is clinically indicated. Only an investigator or medically qualified person can classify a participant's local reaction as Grade 4. If a participant experiences a confirmed Grade 4 local reaction, the investigator must immediately notify the sponsor and, if it is determined to be related to the administration of the study intervention, further vaccinations will be discontinued in that participant.

PFIZER GENERAL BUSINESS

Table 4.	Local Reaction (Grading Scale for H	'articipants >12 Ye	ars of Age (at Visit 1)

	Mild (Grade 1)	Moderate (Grade 2)	Severe (Grade 3) ^a	Potentially Life-Threatening (Grade 4) ^b
Pain at the injection site	Does not interfere with activity.	Interferes with activity.	Prevents daily activity.	Emergency room visit or hospitalization for severe pain.
Redness	>2.0 cm to 5.0 cm (5 to 10 measuring device units).	>5.0 cm to 10.0 cm (11 to 20 measuring device units).	>10 cm (≥21 measuring device units).	Necrosis or exfoliative dermatitis.
Swelling	>2.0 cm to 5.0 cm (5 to 10 measuring device units).	>5.0 cm to 10.0 cm (11 to 20 measuring device units).	>10 cm (≥21 measuring device units).	Necrosis.

a. For participants experiencing local reactions >14 measuring device units (>7 cm), a telephone contact should occur to determine if an unscheduled visit may be required.

Table 5. Local Reaction Grading Scale for Participants ≥2 to <12 Years of Age (at Visit 1)

	Mild (Grade 1)	Moderate (Grade 2)	Severe (Grade 3) ^a	Potentially Life-Threatening (Grade 4) ^b
Pain at the injection site	Does not interfere with activity	Interferes with activity	Prevents daily activity	Emergency room visit or hospitalization for severe pain at the injection site
Redness	0.5 to 2.0 cm (1 to 4 measuring device units)	>2.0 to 7.0 cm (5 to 14 measuring device units)	>7 cm (>14 measuring device units)	Necrosis or exfoliative dermatitis
Swelling	0.5 to 2.0 cm (1 to 4 measuring device units)	>2.0 to 7.0 cm (5 to 14 measuring device units)	>7 cm (>14 measuring device units)	Necrosis

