a. For participants experiencing local reactions >14 measuring device units (>7 cm), a telephone contact should occur to determine if an unscheduled visit may be required.

PFIZER GENERAL BUSINESS

b. Only an investigator or qualified designee can classify a participant's local reaction as Grade 4, after clinical evaluation of the participant or documentation from another medically qualified source (eg, emergency room or hospital record). Grade 4 local reactions will be collected on the AE case report form and assessed by the investigator using the AE intensity grading scale as detailed in the protocol (Section 10.2.3).

b. Only an investigator or qualified designee can classify a participant's local reaction as Grade 4, after clinical evaluation of the participant or documentation from another medically qualified source (eg, emergency room or hospital record). Grade 4 local reactions will be collected on the AE case report form and assessed by the investigator using the AE intensity grading scale as detailed in the protocol (Section 10.2.3).

For each local reaction reported for each dose, the maximum severity grade will be derived for the e-diary collection period (Day 1 through Day 7, where Day 1 is the day of each dose) as follows:

maximum severity grade = highest grade (maximum severity) within 7 days after vaccination (Day 1 through Day 7) among severity grades where the answers are neither "no" nor missing for at least 1 day during the interval from Day 1 through Day 7.

If a local reaction is captured in more than 1 data source, eg, e-diary, unplanned assessment, and/or the AE CRF, the highest grade (maximum severity) across all sources will be used in the summary.

Duration (First to Last Day Reported)

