3.1.2.2. Systemic Events (Systemic Event Symptoms and Fever)

The systemic events assessed and recorded in the e-diary are fever, vomiting, diarrhea, headache, fatigue/tiredness, chills, new or worsened muscle pain, and new or worsened joint pain from Day 1 through Day 7, where Day 1 is the day of each dose. The e-diary entries from the participant and unplanned clinical assessments within 7 days after vaccination will be the primary data source for these events. In addition, any AEs recorded on the AE CRF that are considered systemic events starting within 7 days after vaccination will be consolidated with e-diary data and included in the reactogenicity report. The derivations for systemic events will be handled in a way similar to the handling of local reactions with respect to presence of event; severity level, duration, and onset day (see Section 3.1.2.1).

PFIZER GENERAL BUSINESS

The variables associated with the systemic events will be computed in a way similar to the way local reactions are computed (see Section 3.1.2.1).

The symptoms will be assessed by the participant as absent, mild, moderate, or severe according to the grading scale in Table 6. For events recorded in the AE CRF that are considered systemic events and consolidated with e-diary data, the severity will be based on the AE intensity grade recorded in the CRF.

Table 6. Systemic Event Grading Scale

	Mild (Grade 1)	Moderate (Grade 2)	Severe (Grade 3) ^a	Potentially Life-Threatening (Grade 4) ^b
Vomiting	1-2 times in 24 hours.	>2 times in 24 hours.	Requires IV hydration.	Emergency room visit or hospitalization for hypotensive shock.
Diarrhea	2 to 3 loose stools in 24 hours.	4 to 5 loose stools in 24 hours.	6 or more loose stools in 24 hours.	Emergency room visit or hospitalization for severe diarrhea.
Headache	Does not interfere with activity.	Some interference with activity.	Prevents daily routine activity.	Emergency room visit or hospitalization for severe headache.
Fatigue/tiredness	Does not interfere with activity.	Some interference with activity.	Prevents daily routine activity.	Emergency room visit or hospitalization for severe fatigue.
Chills	Does not interfere with activity.	Some interference with activity.	Prevents daily routine activity.	Emergency room visit or hospitalization for severe chills.

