New or worsened muscle pain	Does not interfere with activity.	Some interference with activity.	Prevents daily routine activity.	Emergency room visit or hospitalization for severe new or worsened muscle pain.
New or worsened joint pain	Does not interfere with activity.	Some interference with activity.	Prevents daily routine activity.	Emergency room visit or hospitalization for severe new or worsened joint pain.

Abbreviation: IV = intravenous.

- a. For participants experiencing severe systemic events, a telephone contact should occur to determine if an unscheduled visit may be required.
- b. Only an investigator or qualified designee can classify a participant's systemic event as Grade 4, after clinical evaluation of the participant or documentation from another medically qualified source (eg, emergency room or hospital record). Grade 4 systemic events will be collected on the AE case report form and assessed by the investigator using the AE intensity grading scale as detailed in the protocol (Section 10.2.3).

PFIZER GENERAL BUSINESS

Oral temperature will be collected in the evening, daily, for 7 days following each dose (Days 1 through 7, where Day 1 is the day of each dose) and at any time during the 7 days that fever is suspected. Fever is defined as an oral temperature of $\geq 38.0^{\circ}$ C (100.4°F). The highest temperature for each day will be recorded in the e-diary.

Temperature will be measured and recorded to 1 decimal place. Temperatures recorded in degrees Fahrenheit will be programmatically converted to degrees Celsius for reporting. Temperatures <35.0°C and >42.0°C will be excluded from the analysis. Fever will be grouped into ranges for the analysis according to Table 7 below.

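### A reaction confirmed as Grade 4 under SAP Tables 4 to 6 may be tabulated at a lower grade, because the SAP takes AE-CRF severity from a different scale

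*SAP*

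**What the plan says.** Two severity scales feed one reactogenicity summary.

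- **Event tables.** SAP Tables 4 to 6 (Protocol Tables 3 to 5) define Grade 4 mostly by what happened. For injection-site pain it is "Emergency room visit or hospitalization for severe pain"; for headache it is "Emergency room visit or hospitalization for severe headache". Fatigue, chills, muscle pain, joint pain and diarrhea follow the same pattern.
- **AE intensity scale.** In Protocol 10.2.3, Grades 1 to 3 depend on how far usual function is disturbed. Grade 4 is "Life-threatening consequences; urgent intervention indicated".

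The e-diary cannot supply Grade 4. Protocol 8.2.4.3 limits the diary entry: "The symptoms will be assessed as absent, mild, moderate, or severe according to the grading scale in Table 5". Only an investigator or qualified designee may assign Grade 4, and footnote b to the tables lets an emergency room or hospital record support that classification.

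Footnote b then sends these events to the AE CRF. In SAP 3.1.2.1, "Grade 4 local reactions will be collected on the AE case report form and assessed by the investigator using the AE intensity grading scale"; in SAP 3.1.2.2, "Grade 4 systemic events will be collected on the AE case report form and assessed by the investigator using the AE intensity grading scale".

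For AE-CRF events counted as local reactions, SAP 3.1.2.1 states that "the severity will be based on the AE intensity grade recorded in the CRF". SAP 3.1.2.2 applies the same rule to AE-CRF events that are "considered systemic events and consolidated with e-diary data, the severity will be based on the AE intensity grade recorded in the CRF". When an event appears in several sources, both sections use the highest grade found in any of them.

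**The concern.** The two Grade 4 definitions are not the same, and the SAP gives no mapping between them. An emergency room visit for severe headache is enough for Grade 4 in Table 6, but it need not have life-threatening consequences. The SAP has no rule that keeps the table-based Grade 4 when the same event carries a lower AE intensity grade.

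Local reactions and systemic events are primary safety endpoints, and SAP 6.1.2.1.1 and 6.1.2.2.1 present them by maximum severity. What is at stake is whether the Grade 4 row counts the Grade 4 that the documents define. Because AE-CRF events are merged with diary data, participants in one row may also have been graded on different scales.

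**Working it through.** The plan gives no figure to reproduce. The check follows one event through the rules and then illustrates the size.

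**Tracing an event.** Take a participant seen in an emergency room for severe headache within 7 days of a dose.

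1. *Table 6:* Grade 4, because the emergency room visit meets the criterion.
2. *E-diary:* severe at most, so Grade 3 at most.
3. *Unplanned assessment:* Protocol 8.10 has the investigator grade systemic events and injection-site pain on the event tables at the unscheduled visit, so Grade 4 can be recorded there. However, a suspected Grade 4 may be handled by telephone or by a visit. The visit is also waived if the event has resolved, the participant cannot attend, the diary entry was wrong, or the investigator judges it unnecessary.
4. *AE CRF:* graded on the Protocol 10.2.3 scale. The investigator may choose Grade 4 or, if the effect was significant interference with function without life-threatening consequences, Grade 3.
5. *Reported grade:* the maximum over items 2 to 4.

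| Unplanned assessment recorded Grade 4? | AE intensity assigned | Reported grade |
|---|---|---|
| Yes | Any | 4 |
| No | 4 | 4 |
| No | 3 | 3 |
| No | Below 3 | 3 if the diary says severe, otherwise lower |

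The table-based Grade 4 is lost only in the last two rows. The any-severity count is the same in all four.

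The same trace applies to injection-site pain under SAP 3.1.2.1. It does not apply in the same way to fever, which is grouped by temperature range (SAP Table 7).

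**Illustration.** Assume one such event in a subset of N participants; no document gives an expected Grade 4 frequency for this trial. Intervals are Clopper-Pearson, as in SAP 5.2.1.

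- 0 of N: upper limit = 1 − 0.025^(1/N). For N = 10: 1 − 0.025^0.1 = 30.8%.
- 1 of N: lower limit = 1 − 0.975^(1/N). For N = 10: 1 − 0.975^0.1 = 0.25%. The upper limit solves (1 − p)^N + N·p·(1 − p)^(N−1) = 0.025. For N = 10 it is 44.5%.

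| N | Grade 4 kept | Grade 4 lost |
|---|---|---|
| 10 (planned minimum per pediatric disease subset in each age group) | 10.0% (0.3 to 44.5) | 0% (0 to 30.8) |
| 15 (whole 12 to <18 age group) | 6.7% (0.2 to 31.9) | 0% (0 to 21.8) |
| 65 (whole 5 to <12 age group) | 1.5% (0.0 to 8.3) | 0% (0 to 5.5) |

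**The case against.** The best defense is that the loss is not automatic. AE Grade 4 also mentions urgent intervention, and the event tables label their own Grade 4 column as potentially life-threatening. An investigator who has just classified a reaction as Grade 4 may well enter AE Grade 4. Protocol 8.10 also makes a site visit the default, and a Grade 4 recorded there survives through the highest-grade rule. All of this stands. It narrows the problem to events with no unplanned assessment at Grade 4, and footnote b allows exactly that when it accepts an emergency room or hospital record.

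Three stronger readings are tempting, and the documents do not support them.

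- *Every Grade 4 reaction that is not life-threatening and comes only through the AE CRF is downgraded.* The scale does not compel Grade 3, so the word is may.
- *Size-based items are generally mis-graded.* Redness of 8 cm in a child is 16 device units (8 / 0.5), above the 14-unit limit, and so Grade 3 in SAP Table 5. If the diary or a visit holds that measurement, the highest-grade rule keeps Grade 3 whatever the AE intensity. A lower grade needs both measurements to be absent.
- *Participant protection is weakened.* Sponsor notification and discontinuation follow the investigator's confirmed classification (Protocol 8.2.4.2 and 8.2.4.3), not the table in the report. A hospitalized case is also an SAE, and SAEs are tabulated and listed.

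Two further points stand. The AE-scale routing is in the protocol footnotes too, so the SAP did not create the conflict. And the SAP version history says these sections were revised for a reactogenicity approach that the FDA requested. The documents do not describe that request, so whether it covers the severity rule cannot be checked.

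**Conclusion.** The point holds in a limited form. The rules as written allow a reaction confirmed as Grade 4 under SAP Tables 4 to 6 to appear as Grade 3 or lower. Two conditions must both be met: no unplanned assessment recorded Grade 4, and the investigator assigned a lower AE intensity. The effect is confined to the maximum-severity split of a primary safety endpoint.

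The number of affected events is likely to be small, but it cannot be estimated from the documents. Under the assumption of one event in 10 participants, the Grade 4 estimate moves from 10% to 0%, with wide and overlapping intervals in a descriptive study. The practical consequence is that a reaction notified to the sponsor as Grade 4 might not appear in the Grade 4 row. This should be corrected before the tables are produced.

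**What to change.** 1. In SAP 3.1.2.1 and 3.1.2.2, state that any reaction the investigator confirmed as Grade 4 under Tables 4 to 6 is tabulated as Grade 4 whatever its AE intensity grade. The classification should be traceable, because the protocol already requires a confirmed Grade 4 to be notified to the sponsor at once.
2. Footnote reactions whose reported severity rests only on the AE intensity scale. The SAP already does something similar for an AE-CRF fever with no temperature, which it shows with an unknown range.
3. Reconcile footnote b in Protocol Tables 3 to 5 and SAP Tables 4 to 6, so that both say which scale sets the reported grade. Footnote b to Protocol Table 5 also names local reactions under a systemic-event table, where the SAP counterpart names systemic events.
4. Check the wording against the FDA-requested approach cited in the SAP version history.

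Re-grading other AE-CRF events by diameter or stool count is not proposed, because the documents do not show that the AE CRF collects those fields. The cost is SAP wording, the alignment of one protocol footnote, medical review of a few AE-CRF reactions and one table footnote. No participant procedure changes.
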